5.2.2 Blinding

Participants and the health care professionals providing the SAF intervention cannot be blinded to intervention allocation. This may introduce unconscious bias that has the potential to either inflate or deflate the number of reported falls. However, there is no reason to assume that there would be systematic inflation or deflation of falls in either of the two groups. At a minimum, the NCTU team analysing the data and the Chief Investigator (CI) and Deputy Chief Investigator (DCI) will be blinded to the participant randomised intervention.

Study role	Blinding status	Comments				
Participant 1	Not blinded	The participant will know				
		whether they receive the				
		additional SAF intervention				
Principal Investigator and	Not blinded	as well as their usual care. The stroke service staff will				
other stroke service	Not billided	be unblinded to the				
staff (research staff or		treatment allocation either as				
stroke healthcare		part of the study team				
professionals)		randomising and delivering				
		the intervention or as part of				
		the usual care team who				
		could become aware				
		following documentation in				
		patient medical notes or usual care home visits.				
Chief Investigator and I	Blinded	The CI and deputy CI will				
Deputy Chief Investigator	Billided	remain blinded to treatment				
		allocation overall.				
Database Programmer	Not blinded	The database programmer				
		will be responsible for the				
		management of the				
		randomisation system and				
		will have access to unblinded				
		datasets within the study database.				
Study Management staff	Blinded as far as practically	The study management				
	possible	team will remain blinded				
		where possible and not have				
		access to information such				
		as SAF visit data that could				
		unblind them. One or more				
		members of the study				
		management team may take up the role of follow-up				
		coordinator and therefore				
		may be unblinded.				

Page 23 of 53 FISS Protocol Final Version 1.0 date 24-Jul-2025

Follow-up Coordinator	Not blinded	The study follow-up coordinator will not be blinded to study intervention to allow full access to study data to support follow-up telephone calls with participants.
Data Management	Not blinded	Data management staff will have access to the unblinded datasets within the study database to ensure data quality and undertake central monitoring activities. They will have access to all data fields across the SAF intervention participants and usual care.
Study Statistician and Senior Study Statistician	Blinded	The study and senior study statistician will not have access to intervention allocations or data which has the potential to unblind until after the first database lock for the analysis.
Independent Statistician	Not blinded	A statistician, independent to the study team, will be responsible for the generation of closed reports for the Data Monitoring Committee (DMC) and other reports with potentially unblinding data and will therefore be unblinded to study treatment allocations.

Maintenance of randomisation codes and procedures for breaking code

The stroke service staff, Falls Leads and participants (and carers and/or friends/relatives as applicable) will be aware of which arm the participant is randomised to. Therefore, there is no process required for code breaking. NCTU will retain the randomisation codes for participants for the duration of the study.

At their request, the DMC may review unblinded data. This will be prepared by a statistician from NCTU not involved in the study (i.e., an independent statistician), who will store all unblinded output in a secure and access-controlled area.

The study statistician will receive the treatment allocation only after the SAP has been finalised and approved, and the database has been locked.

Page 24 of 53

FISS Protocol Final Version 1.0 date 24-Jul-2025

5.3 STUDY MANAGEMENT

The study is funded by the National Institute for Health and Care Research (NIHR) Health Technology Assessment (HTA) Programme. The Sponsor is the University of Nottingham. The study will be managed from a central coordinating centre at University of Nottingham supported by Nottingham Clinical Trials Unit.

The Chief Investigator (CI) has overall responsibility for the study and shall oversee all study management. The data custodian will be the CI.

5.3.1 Study Committees

Trial Management Group (TMG)

The TMG will meet on a regular basis (approximately monthly) and will be responsible for the day-to-day management of the study. The CI, deputy CI, co-applicants (where required) and representatives from FISS Australia, qualitative and NCTU teams (study management, data management, statistical and health economic representatives) are responsible for the day-to-day management of the study and will form the TMG.

The TMG will ensure high quality study conduct, to time and within budget, monitor all aspects of the conduct and progress of the study, ensure that the protocol is adhered to and take appropriate action to safeguard participants and the integrity of study itself. The TMG will also be responsible for ensuring project milestones are achieved.

Trial Steering Committee (TSC)

The role of the TSC is to maintain oversight of the study, monitor progress and provide advice to the TMG and funder. The TSC will consist of an independent chair, and other independent members with clinical and research expertise including parent representatives. The CI and Study Manager will be non-independent (non-voting) members of the TSC. Other members of the TMG may join TSC meetings (in a non-independent, non-voting capacity) as deemed necessary. Representatives from the funder and Sponsor may be invited to attend as observers.

The TSC will operate in accordance with a study-specific charter (outlining the committee's terms of reference), the funder's guidelines and the relevant NCTU Standard Operating Procedures (SOPs).

The TSC will meet at least once a year during the study, including following completion of a 10-month internal pilot period to review the results of the internal pilot and decide on recommendations regarding study progression. Additional meetings may be called and the TSC may, at their discretion, request to meet more frequently.

The TSC will consider and act, as appropriate, upon the recommendations of the Data Monitoring Committee.

The Data Monitoring Committee (DMC)

The role of the DMC is to give advice on whether the accumulated data from the study, together with the results from other emerging research, justifies the continuing recruitment of participants.

Members of the DMC will be independent of the study and have relevant clinical, statistical and other methodological experience of clinical studies.

The DMC will operate in accordance with a study-specific charter (outlining the committee's terms of reference), the funder's guidelines and the relevant NCTU SOPs.

Page 25 of 53

FISS Protocol Final Version 1.0 date 24-Jul-2025

The DMC will meet at least once a year during the study, including following completion of the 10-month internal pilot phase to review the results of the internal pilot and make recommendations to the TSC on study progression. They will also be responsible for monitoring the data for consistency with the sample size assumptions and recommending, if necessary, a requirement for changes to assumptions which could lead to changes in the planned sample size. Additional meetings may be called, and the DMC may, at their discretion, request to meet more frequently or continue to meet following completion of recruitment. An emergency meeting may also be convened if a safety issue is identified.

The DMC will report directly to the Chair of the TSC who will convey the findings of the DMC to the TSC, TMG and Sponsor as applicable.

5.4 DURATION OF THE STUDY AND PARTICIPANT INVOLVEMENT

Study Duration: Study funding is for 48 months (from the start of contract delivery to final report).

Participant Duration: The participation period for FISS is 12 months following randomisation.

End of the study

The end of study will be the final database lock. The end of participant involvement in the study will be the last data collection (at 12 months post-randomisation) of the last participant. NCTU will notify the Research Ethics Committee (REC) that the study has ended within 90 days of the end of study. Should the study be terminated early, NCTU will inform REC within 15 days of the end of study. NCTU will provide them with a summary of the clinical study report within 12 months of the end of study.

Selection of participants Identification

Participants will be identified from 10 hospital stroke services across the UK which should ensure a diverse mix of participants. Patients who are aged 18 or over who have a confirmed stroke diagnosis (CT or MRI scan) and are potentially eligible will be approached about the FISS study.

Please see section 5.7 for more information on identification of participants and section 5.8 for information on withdrawal/discontinuation/change in participant status.

5.5 SCREENING

The participating stroke services will maintain a list of potentially eligible patients who were identified and approached about the study. Stroke services will enter anonymised data (totals) from the logs monthly into the study database.

The NCTU may request copies of the full screening logs from recruiting stroke services for the purpose of monitoring.

Please see section 6.1 for more information on screening of participants.

5.6 ELIGIBILITY CRITERIA

The target population are patients who have had a confirmed stroke (MRI or CT scan) with planned discharge to their/a home. Eligibility criteria are assessed as part of routine

Page 26 of 53

FISS Protocol Final Version 1.0 date 24-Jul-2025

assessments, no additional study-specific assessments are required to ascertain eligibility for FISS.

5.6.1 Inclusion Criteria

- Aged 18 or over
- Confirmed stroke diagnosis in hospital
- Planned to be discharged to home, (including sheltered accommodation, somebody else's home)*
- Able to report number of falls and study questionnaires either individually or via a carer/family member/personal consultee
- Ability to provide informed consent from participant or personal consultee.

5.6.2 Exclusion Criteria

- Resident of, or being discharged to, a care home
- On end-of-life pathway

*Geographical Eligibility for Participation

Participants must live within the geographical area covered by the participating stroke service delivering the intervention, as determined by postcode. However, the specific postcodes included will vary by stroke service. Each stroke service will decide its eligible geographic criteria based on its standard care approach, some will use the participant's home address, while others will align care with Primary Care Networks (PCNs) and GP practices. This ensures consistency with existing healthcare structures. Individuals residing outside the designated area will not be eligible to take part in the study. Postcode information and any associated restrictions will be included in the localised study information.

If a participant relocates outside the area during the study, they can continue providing monthly falls data and responding to follow-up questionnaires but their continued participation in the SAF intervention will be subject to stroke service discretion. Decisions will be made on a case-by-case basis, depending on service-specific resources and logistics.

Carers eligibility (for completion of the carer questionnaire):

Inclusion Criteria

- Individuals who provide unpaid care and support to a stroke survivor.
- This includes:
 - o Partners or spouses
 - o Family members (e.g., parents, children, siblings)
 - Friends or neighbours
- Carers who assist with daily living tasks, emotional support, coordination of care, or
 other forms of assistance related to the stroke survivor's recovery.

Exclusion Criteria

• Individuals who are paid professionals providing care (e.g., nurses, support workers, personal care assistants).

5.7 INFORMED CONSENT

All participants must provide informed consent prior to participation (or personal consultee advice for those who lack capacity). Informed consent or advice can be taken in person or remotely. The informed consent form (ICF)/electronic ICF (eICF) will be signed and dated by either the participant, witness (in the case of people who have capacity to consent for

Page 27 of 53

FISS Protocol Final Version 1.0 date 24-Jul-2025

themselves but are physically unable to sign a consent form) or personal consultee, prior to any research activity starting. The PI or delegate will explain the details of the study, provide the PIS and ensure that sufficient time is given to consider participation. The PI or delegate will answer any questions that the patient or their carer/family has concerning participation in the study.

In some cases, patients may be discharged from the hospital relatively soon after their stroke, requiring consent to be obtained remotely. These patients should be provided with a FISS discharge pack (including a discharge letter, and the PIS) either at the point of hospital discharge or sent (post or email) to them soon after discharge. This discharge pack can be provided by any member of research staff or FISS trained stroke healthcare professionals. The discharge pack will include contact details of the local research team, allowing potential participants to easily contact them if they wish to express their interest in taking part or ask any questions.

Stroke services will be asked to contact all potential participants (previously provided with a discharge pack) to provide further information and ask if they would be interested in participating. For individuals who are interested in joining the study but are unable to use their phone or experience difficulties in doing so, an appropriately delegated member of the stroke service is able (where possible) to visit them at home to facilitate the consent process.

Consent (in person or remote) should be completed as soon as possible, but no later than 28 days post-discharge. To ensure patient eligibility, the individual obtaining consent will ask the patient to provide their discharge date (patient-reported).

For participants who provided consent in a hospital or inpatient rehabilitation unit, if the time from consent date exceeds 28 days at the time of randomisation, they must confirm that they are still happy to take part in the study. This confirmation will be obtained at the point of baseline/randomisation and documented in the Research Electronic Data Capture system (REDCap).

Participants will have the option to provide consent to receive a summary of the study results when available and to be contacted about participation in the process evaluation interviews (information on these interviews and who will be contacted to participate will be provided in the PIS).

5.7.1 Written Informed Consent

Paper ICFs will be completed by the patient and the PI or delegate. Patients must tick each consent point and sign and date the consent form. Optional consent points will require a tick in a 'Yes' or 'No' box. The researcher who is taking consent must verify and countersign the form at the point the patient signs the consent form. The patient must be given a copy of the paper consent form, a copy must be filed as part of their medical records and a copy scanned and uploaded to the REDCap database for NCTU review. In person consent can be completed electronically (e-consent) where appropriate.

For individuals unable to complete remote consent electronically (see section below), written informed consent must be obtained in person at the participant's home address. During the same visit, the baseline questionnaire and randomisation process can also be completed. However, e-consent will be prioritised unless the participant encounters difficulties preventing its use.

Page 28 of 53

FISS Protocol Final Version 1.0 date 24-Jul-2025

5.7.2 Electronic Consent (e-Consent)

E-consent can be used to consent patients to the study remotely. If e-consent is being used remotely then the PIS and eICF will be sent electronically (by SMS or email) via a hyperlink. After the patient has had the opportunity to read and consider the study, they must then tick a box against each statement to indicate they are giving fully informed consent for each element of the eICF. They must then complete their name and electronically sign the form. Returned electronic consent forms are then verified and countersigned by the investigator or delegate. A copy of the fully signed eICF is then sent to the participant and the participating stroke service by email. A copy will be filed in the participant's medical notes.

5.7.3 Additional consent options

Witnessed Consent

Patients who are eligible and are deemed to have the capacity to consent, but who cannot sign a consent form (e.g. due to significant sight loss or dexterity issues) may give verbal consent to the study to the PI or delegate. This will be recorded on the 'witness consent' section of the participant consent form by a member of the research team. This consent will be witnessed by an independent witness who will countersign the consent form. Witnessed consent must be completed in person and cannot be completed via remote e-consent.

Consent for participants without capacity If a patient is deemed not to have capacity to consent, then a personal consultee will be approached to provide advice to the researcher on the patient's wishes and feelings regarding participation in the study. The personal consultee will be a person that the patient has a close personal relationship with (e.g., a family member or friend) or person with lasting power of attorney. The personal consultee will be provided with a consultee declaration form and the PI or delegate will explain the details of the study. The personal consultee will have time to consider participation on the patient's behalf and have the opportunity to ask questions. A signed consultee declaration form (paper or by e-consent) will then be collected from the personal consultee before the participant can undergo any interventions related to the study.

Continued participation is voluntary, and the participant is free to withdraw from the study should they wish. Withdrawal will be clearly documented in the participant's medical records and the study database.

Documenting consent

Once the participant is entered into the study, the participant's unique study identification number will be entered on the ICF that is kept in the Investigator Site File (ISF). One copy of the ICF will be provided to the participant (or personal consultee), one copy will be filed in the medical notes, one copy will be uploaded electronically in the study database for central monitoring by NCTU, and where paper consent is recorded, the original will be placed in the ISF.

Details of the informed consent discussions will be recorded in the participant's medical notes. This will include date of discussion, the name of the study, version number of ICF signed and the date consent received. Where consent is obtained on the same day that the study related assessments are due to start, a note will be made in the medical notes as to what time the consent was obtained and what time the procedures started.

Should there be any subsequent amendment to the final protocol, which might affect a participant's participation in the study, continuing consent will be obtained using an amended Consent form which will be signed by the participant.

Page 29 of 53

FISS Protocol Final Version 1.0 date 24-Jul-2025

5.8 RECRUITMENT

5.8.1 Expected duration of participant participation

Participants will be involved in the study for 12 months once randomised. Active participation ends once the participant completes the final set of questionnaires and falls reporting at 12 months, or as soon as possible thereafter.

5.8.2 Co-enrolment

There is a chance that patients may be approached for participation who are already enrolled in another clinical trial or study. Co-enrolment alongside FISS may be acceptable. Decisions on co-enrolment will be approved on a case-by-case basis following discussions with the participating stroke service staff responsible for assessing eligibility and the FISS CI or deputy CI.

5.8.3 Removal of participants from therapy or assessments /participant withdrawal

Participants (and personal consulteess where appropriate) are free to withdraw consent at any time during the study, without giving a reason and without impacting their usual NHS care. Participants will be encouraged to discuss reasons for withdrawal with staff to determine whether discontinuation from a specific study activity may be more appropriate.

Participants will be made aware (via the information sheet and consent form) that should they withdraw, the data collected to date cannot be erased and may still be used in the final analysis. In accordance with the guidance for researchers, we will attempt to minimise the number of participants withdrawing consent (PeRSEVERE project[17]).

Participants are able to withdraw from the study at any time. Withdrawal from the study means discontinuation of all trial activities and communications (including results). If a participant wants to continue in the study but discontinue a specific activity (e.g. no longer receive text messages) their participation status could be amended. Activities that could change a participant's status are outlined in Table 5.

Table 5: Change in participant status

Activity type	Discontinuation procedure	Use of data that is already collected					
Discontinue from receiving study intervention.	Participants who discontinue from the study intervention will remain in the study and their data will be collected as per protocol, unless they explicitly state otherwise. Post-request no further intervention visits or phone calls will take place.	Data collected will be retained and used.					
Discontinue from completing follow-up questionnaires (3, 6, 9 or 12 months) but willing to continue with monthly falls reporting.	Participants who discontinue from completing questionnaires at any of the 3, 6, 9 and 12 month timepoints will remain in the study. These questionnaires will not be sent to the participant. Monthly falls	Any data collected prior to request (i.e. data obtained at baseline or previous questionnaires) will be retained and used.					

Page 30 of 53

FISS Protocol Final Version 1.0 date 24-Jul-2025

	data will continue to be collected as per protocol.	
Discontinue from other study communications.	Any patient who requests to be withdrawn from other study communications will be removed from all mailing lists for ongoing study contact (e.g. newsletters and reminders) but will still receive study questionnaires. Study data will continue to be collected as per protocol.	Data collected will be retained and used.
Discontinue from reporting monthly falls data or full study withdrawal.	Any participant that requests to stop completing primary outcome data or requests have no further involvement in the study will be marked as withdrawn on the study database. No further questionnaires will be sent to the participant, and no further data (including monthly falls data) will be collected.	Any data collected prior to participant withdrawal will be retained and used. No further data will be collected.

[figure not shown]
Participating stroke services may withdraw participants from the study at their own request, request of a personal consultee or at the discretion of a stroke healthcare professional.

Any change in participant status must be completed within REDCap. Additional support can be provided by the NCTU research team as required.

Withdrawn participants will not be replaced. The sample size has allowed for up to 10% non-collection of primary outcome data.

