7.2.2 Sample size and justification

We assume that stroke survivors will have an annual falls rate somewhere between that in community dwelling stroke survivors up to 5 years post stroke in the FAST study (1.8 falls per year) and that of participants in care homes observed in the FinCH study (3.2 falls per year). Using the upper limit of the 95% confidence interval for the overdispersion parameter (FinCH study; 1.1) and assuming an annual falls rate of 2.5 falls per year per participant, 416 evaluable participants would be required to detect a relative difference of 33% in falls rates (i.e. to 1.675 falls per year) using a negative binomial model, with 90% power at the 5% significance level (2-sided) – or 208 per arm. Sample size calculations were performed using PASS 2022 (NCSS).

This difference was deemed a clinically important difference by our FISS PPI group and in the FinCH study. A survey of occupational health professionals showed that 15/27 (58%) would consider adoption of the SAF program if the falls rate was reduced from 3 to 2 falls per year (a 33% reduction), with 3/27 (11.5%) saying they would not consider adoption.

The negative binomial model takes into account exposure, but there is a risk that no robust primary outcome data are collected from some individuals. Therefore, we will inflate the sample size by 10% and aim to randomise 464 participants, or 232 per arm. This sample size also provides 90% power to detect a relative difference of 34% and 36% if the falls rate was lower than expected at 2 and 1.5 falls/year.

The primary outcome event rate is based on the best evidence currently available. However, we recognise that it is an estimate, and our assumptions will be monitored by the DMC throughout the study. They will advise whether a sample size adjustment is necessary.

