7.2.6 Definition of populations analysed

Intention to treat dataset: All randomised participants are summarised/analysed according to their randomised treatment irrespective of the treatment(s) they actually received. This is the primary dataset to be used in all analyses unless stated otherwise in the SAP.

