11. ADVERSE EVENTS

Adverse events (serious and non-serious) will not be collected in this study. Falls and falls severity will be specifically collected as primary and secondary outcomes monthly.

This is a low-risk intervention. No specific risks, untoward incidents or adverse events were reported during feasibility work. If participants become distressed during the SAF assessment or when completing the checklist and suggested actions, the process will be halted until the participant assessed as to whether they can continue with the intervention. The participant has the right to decline any intervention at any time.

Fall rates will be monitored for harm and reported to the DMC and TSC. The DMC and TSC have the ability to recommend changes to the study protocol if fall rates are substantially higher than expected. The DMC will review unblinded safety data including reported frequencies of primary and secondary outcomes by treatment arm annually. This will be provided by the NCTU via a secure email.

SAF assessments and or/actions may be stopped in the event that the participant shows evidence of distress. This will be documented. However, the participant will not be withdrawn from the study.

As the SAF intervention is copyrighted by the University of Nottingham, it is responsible for any issues which arise due to the design of the intervention, training given to SAF leads or any issues with the tool itself.

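### Table 5 has no option to stop only the monthly falls reports and keep the questionnaires, and service staff may withdraw participants from the whole study without stated criteria

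*Protocol*

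**What the plan says.** Protocol 5.8.3 distinguishes withdrawal, which ends every trial activity and communication, from stopping one activity. It asks staff to explore the second before accepting the first, and commits to keeping withdrawals of consent to a minimum. Table 5 then lists the partial options.

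- **Stopping the intervention:** the participant stays in and data collection continues.
- **Stopping the questionnaires but still reporting falls:** "Participants who discontinue from completing questionnaires at any of the 3, 6, 9 and 12 month timepoints will remain in the study".
- **Stopping other communications:** the participant stays in and questionnaires are still sent.
- **Stopping the falls reports, or leaving altogether (one shared row):** "Any participant that requests to stop completing primary outcome data or requests have no further involvement in the study will be marked as withdrawn". No more questionnaires are sent and nothing further is collected. Data gathered up to that point are kept and used.

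Below the table, services may withdraw a participant from the study at the participant's own request, at a personal consultee's request, or "at the discretion of a stroke healthcare professional". No criteria are given for the third route.

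Section 5.2.2 lists stroke service staff as not blinded. Section 7.2.6 defines the analysis set: "All randomised participants are summarised/analysed according to their randomised treatment irrespective of the treatment(s) they actually received". Section 11 covers a participant distressed by SAF assessments or actions, which may be stopped: "However, the participant will not be withdrawn from the study".

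**The concern.** Two separate matters sit in the same section.

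**The shared row.** Falls reporting and the questionnaires serve different outcomes and follow different schedules. A participant may drop the second and keep the first, but not the other way round. Someone who is tired of monthly contact but content to fill in a quarterly pack can only be recorded as withdrawn. What is at stake is the secondary outcomes and the economic evaluation. Section 8.4 would then multiply impute values that might simply have been asked for.

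**Discretionary withdrawal.** The third route ends outcome collection, not just SAF, and is open to people who know the allocation. Contact with the service is not symmetric. Under 4.3, only SAF participants have scheduled Falls Lead sessions, and one session can be triggered by a first fall. If discretion were ever used in a way that tracked arm or fall risk, falls data would be missing for that reason. The primary analysis uses observed data without imputation (7.2.3, 7.2.5). Its exposure term corrects for shorter follow-up, not for who leaves.

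**Working it through.** **1. The rows of Table 5 side by side**

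| Participant wishes to stop | Own row? | Falls reports continue? | Questionnaires continue? |
|---|---|---|---|
| SAF only | yes | yes | yes |
| Questionnaires only | yes | yes | no |
| Other communications only | yes | yes | yes |
| Falls reports only | no, shared with full withdrawal | no | no |
| Everything | shared row | no | no |

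The fourth line is the gap. No other section fills it.

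**2. What one such participant loses** (schedule from Table 6 and 6.2.2 to 6.2.3)

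| Request made | EQ-5D-5L and resource use not collected | NEADL, Short FES-I and PHQ not collected |
|---|---|---|
| before month 3 | 4 of 4 | 2 of 2 |
| months 3 to 6 | 3 of 4 | 2 of 2 |
| months 6 to 9 | 2 of 4 | 1 of 2 |
| months 9 to 12 | 1 of 4 | 1 of 2 |

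**3. How many.** The protocol gives no rate for this pattern. As an assumed range of the 464 randomised: 1% is 4.6, 5% is 23.2 and 10% is 46.4. The top of that range equals the whole 10% allowance in 5.8.3 for uncollected primary outcome data, so it is generous.

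**4. The plan's own sample size** (7.2.2). Inputs: "assuming an annual falls rate of 2.5 falls per year per participant" (control rate 2.5), 1.675 under SAF (ratio 0.67), overdispersion 1.1, one year, two-sided 5%, 90% power.

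- n per arm = [1.960 × √V0 + 1.282 × √V1]² / (ln 0.67)²
- V1 = 1/2.5 + 1/1.675 + 2 × 1.1 = 3.197
- V0, at the mean rate 2.0875, = 2/2.0875 + 2.2 = 3.158
- n = (3.483 + 2.291)² / 0.1604 = 207.9, so 208 per arm and 416 in total, as stated
- 208 / 0.9 = 231.1, so 232 per arm and 464 in total, as stated

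**5. Does withdrawal threaten power?** For 232 per arm, with a fraction w leaving at time t, the information in an arm with rate λ is 232 × [(1 − w)λ/(1 + 1.1λ) + w·tλ/(1 + 1.1tλ)].

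| Withdrawn (assumed) | No falls data at all | Leave at 3 months |
|---|---|---|
| 0% | 92.7% | 92.7% |
| 10% | 89.9% | 91.4% |
| 20% | 86.2% | 90.0% |

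Power is a minor matter here.

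**6. Could discretionary withdrawal bias the rate ratio?** This is an illustration only. It assumes withdrawals confined to people above the median fall risk, a true ratio of 1.0, and a fitted negative binomial model with exposure.

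| Withdrawn, SAF / usual care | No data | Leave at 1 month | 3 months | 6 months |
|---|---|---|---|---|
| 10% / 10% | not run | 0.998 | 0.998 | 0.999 |
| 10% / 5% | 0.953 | 0.953 | 0.974 | 0.976 |
| 15% / 5% | 0.910 | 0.944 | 0.960 | 0.986 |
| 20% / 10% | 0.894 | 0.918 | 0.963 | 0.984 |

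The 1, 3 and 6 month columns come from single simulated runs of 40,000 per arm. Their standard error on the log scale is about √((2/2.5 + 2.2)/40,000) = 0.009, so differences of 0.01 to 0.02 mean little. The shift needs unequal withdrawal that also depends on risk, and it is largest when people leave very early. Its direction here follows from assuming more withdrawal under SAF; the reverse assumption would reverse it.

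**The case against.** **The shared row depends on the participant's own request.** A reader might infer that unblinded decisions drive the whole problem. They do not. Staff decisions enter only through the discretion sentence. Nor does silence trigger the row: 4.4 provides reminders and up to two follow-ups a month, and no section makes a non-responder withdrawn. This stands.

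**Nothing collected is thrown away.** A reader might take the row to mean that data are discarded. Table 5 says that earlier data are retained and used. The loss is of data never requested.

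**The monthly report may not be the heavier task.** It is tempting to say that it is the element most likely to be dropped, since there are 12 reports against four packs. But 6.2.1 asks at most three questions a month, whereas the 6 and 12 month packs hold the 22-item NEADL, the 7-item Short FES-I, PHQ, EQ-5D-5L and resource use. The protocol has no evidence either way, so giving priority to the existing partial option was reasonable. That does not explain why the mirror option is absent.

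**The routes to discretionary withdrawal are narrow, and mitigations exist.** Stopping SAF and distress during SAF both leave the participant in the study. The primary model uses partial follow-up, and 7.2.3 and 7.2.5 plan sensitivity analyses and an assessment of missingness. A trial that enrols people without capacity may also have good reason to keep some discretion. All of this stands and limits the second matter. Sensitivity analyses cannot, however, recover reports that were never sought.

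**Conclusion.** Both rules are in the protocol as described, and nothing elsewhere limits them. Applied as written, the shared row loses secondary and economic data from participants who may be willing to give them, which runs against the section's own preference for stopping a single activity. The size is unknown: the 5 to 46 people above rest wholly on an assumed 1% to 10%.

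The discretion sentence carries a plausible but unquantified risk of falls data missing in relation to arm or fall risk. A reader might infer that the primary estimate is materially biased. The documents do not support that. No rate or pattern of discretionary withdrawal is given. Under the deliberately adverse assumptions above, a null effect is fitted at about 0.96 to 0.97 when people leave at 3 months and about 0.98 to 0.99 at 6 months, against a design ratio of 0.67. Larger shifts need almost no data before withdrawal.

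This is a cheap improvement worth making early, because self-reported data not requested at the time cannot be obtained later. It is not an error in the primary analysis or the sample size, and the trial does not depend on it.

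**What to change.** 1. **Split the last row of Table 5.** (i) Stops monthly falls reports only: the participant stays in the study, still receives the 3, 6, 9 and 12 month questionnaires, and falls exposure ends at the last report. (ii) Full withdrawal, as now.
2. **Qualify the discretion sentence.** State that a professional-led decision does not by itself end outcome collection unless the participant or personal consultee asks for this, or a reason is recorded. An outright ban on professional discretion is not needed.
3. **Reconcile that sentence** with the Table 5 row on stopping the intervention and with section 11, both of which keep the participant in the study.

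The cost is protocol wording, one more category on the participant-status form in REDCap, and a few more questionnaires sent through the existing process. The sample size and the primary model do not change.
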